7.2.4 Follow-up of Abnormal Laboratory Test Values

In the event of unexplained clinically significant abnormal laboratory values, the tests should be repeated and followed up until they have returned to baseline values and/or an adequate explanation of the abnormality is found. If a clear explanation is established, it should be recorded in the eCRF.

7.2.5 Pregnancy

It is not known what effects sebelipase alfa has on human pregnancy or development of the embryo or fetus. Therefore, female patients participating in this study should avoid becoming pregnant, and male patients should avoid impregnating a female partner. Nonsterilized female patients of reproductive age group and male patients must agree to use a highly effective and approved contraceptive method(s) for the duration of the study and to continue to use for 30 days after the last dose of IMP. Highly effective methods of contraception are defined in Section 4.3. Regular pregnancy tests will be performed as defined in Section 5.1.10.

A female subject or a male subject with a female partner must immediately inform the Investigator if she becomes pregnant during the study. The female subject must not receive further sebelipase alfa infusions. Pregnancies occurring up to 90 days after the completion of the last infusion must be reported to the Investigator. The Investigator must report all pregnancies to the Sponsor within 24 hours of notification. The Investigator should counsel the subject discussing the risks of continuing with the pregnancy and the possible effects on the fetus. Monitoring of the subject should continue until conclusion of the pregnancy.

7.3 Recording of Adverse Events

At each scheduled contact with the subject, the Investigator must seek information on AEs by specific questioning and, as appropriate, by examination. Information on all AE should be recorded in the source document, and also in the appropriate AE module of the eCRF. All clearly related signs, symptoms, and abnormal diagnostic procedure results should be recorded in the source document, grouped under one diagnosis.

Page 42 of 76

The date/time when the AE started and stopped, severity, seriousness, action taken with regard to the study drug, causality assessment, and outcome of the event will be recorded in the eCRF for each AE.

Any AEs/SAEs remaining unresolved after completion of the last scheduled visit (i.e., follow-up visit) should be recorded as ongoing in the eCRF. Ongoing AEs/SAEs should continue to be followed up for the period specified in Section 7.2.3, but without further recording in the eCRF. However, follow-up information on SAEs must be reported to the Sponsor as described in Section 7.4.

7.4 Reporting of Serious Adverse Events, Infusion Associated Reactions and Unanticipated Problems

Investigators and the Sponsor must conform to the AE reporting timelines, formats and requirements of the various entities to which they are responsible. At a minimum the events that must be reported are those that are:

- related to study participation,
- unexpected, and
- serious or involve risks to subjects or others (see definitions, Section 7.1).

If the SAE/IAR report is supplied as a narrative, the minimum necessary information to be provided at the time of the initial report includes:

- Protocol number
 •
- Investigator name and site number
- Subject number
- A description of the event
- Date of onset
- Time and amount of last IMP administration

- Current status
- Whether study treatment was discontinued
- The reason why the event is classified as serious (if an SAE)
- Investigator assessment of the relationship between the event and study treatment
- Severity

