7.2.2 Adverse Event Reporting Period

The study period during which AEs must be reported is defined as the period from the signature of written consent to the end of the study treatment follow-up. For this study, AEs will be reported from the date of written informed consent until completion of the follow-up visit at approximately 30 days after the last dose of IMP. If a subject experiences an SAE that is considered to be related to study treatment at any time after the study, it must be reported to the Sponsor.

Page 41 of 76

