7.2.3 Treatment and Follow-up of Adverse Events

Treatment of AEs is at the discretion of the Investigator and should follow the standards of medical care at the Investigator's institution.

All AEs and SAEs will be followed until resolution, the condition stabilizes, or the Investigator and Sponsor agree that follow up is no longer necessary. SAEs that are ongoing after completion of the last scheduled visit should continue to be followed up to determine the final outcome. Non-serious AEs that are ongoing after completion of the last scheduled visit should be followed up until the event resolves or stabilizes, or for a minimum of 30 days after the last dose of IMP (whichever occurs first). Rules for AE/SAE follow-up apply to all subjects, including those withdrawn prematurely, to the extent allowed by the subject's consent.

The Investigator will ensure that AE/SAE follow-up includes further investigations consistent with appropriate medical management and subject consent to elucidate the nature and/or causality of the AE/SAE.

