11.2 Adverse Events

An AE is any untoward medical occurrence in a subject, which does not necessarily have to have a causal relationship with the administration of a pharmaceutical product. An AE can therefore be any unfavorable and unintended sign, symptom or disease temporally associated with the use of the medicinal product, whether or not considered related to the medicinal product. Pre-existing conditions that worsen in severity during the course of the study are to be reported as AEs.

Severity of AEs will be graded on a 5-point scale (mild, moderate, severe, life-threatening and death) according to National Cancer Institute (NCI) Common Terminology Criteria for Adverse Events (CTCAE), version 4.03. All AEs will be coded using the Medical Dictionary for Regulatory Activities (MedDRA[®]), version 13.1 or higher.

In AEsummaries, subjects will only count in one column.

For counting events, if a subject experiences the same AE multiple times, each occurrence of this event will be counted toward the frequency of events; but for counting subjects, each subject will be counted only once within each PT and each SOC. If a subject experiences more than one AE within a PT or SOC, only the AE with the strongest relationship or the greatest severity, as appropriate, will be included in the summaries of relationship and severity, respectively.

A data listing of all AEs reported in the study will be presented.

Additionally a data listing of deaths and AEs leading to study discontinuation will be provided.

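### SAEs unresolved at the follow-up visit are frozen as ongoing in the eCRF, and nothing requires a later-known fatal outcome to reach the SAE and death listings

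*Protocol*

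**What the plan says.** **Collection window.** Protocol 7.2.2: "AEs will be reported from the date of written informed consent until completion of the follow-up visit at approximately 30 days after the last dose".

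**The eCRF record at the end of the window.** Protocol 7.3 asks for the outcome of each AE in the eCRF. For events still open it then says: "Any AEs/SAEs remaining unresolved after completion of the last scheduled visit (i.e., follow-up visit) should be recorded as ongoing in the eCRF". The next sentence is: "Ongoing AEs/SAEs should continue to be followed up for the period specified in Section 7.2.3, but without further recording in the eCRF".

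**Follow-up after the window.** Protocol 7.2.3: "SAEs that are ongoing after completion of the last scheduled visit should continue to be followed up to determine the final outcome". For this, 7.3 gives a route outside the eCRF: "However, follow-up information on SAEs must be reported to the Sponsor as described in Section 7.4". Section 7.4.1 describes that route as an SAE form sent to the Sponsor, with significant new information due within 24 hours of the investigator learning of it.

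**Planned outputs.** Protocol 8.7.1 includes severity and outcome in the by-subject event listings and tabulates by greatest severity. SAP 11.2 uses a five-point scale that ends in death and summarises severity by the worst grade. It adds: "Additionally a data listing of deaths and AEs leading to study discontinuation will be provided". SAP 11.2.1 plans SAE counts, incidence and a listing. None of these sections names a data source, an outcome cutoff or a reconciliation step. SAP 5.3 says data are analysed as they stand in the database.

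**The concern.** The protocol asks sites to find out how an unresolved SAE ended, then closes the record that would carry the answer. The Sponsor can hold a fatal outcome while the study's outputs show the same event as unresolved.

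The closing rule fits non-serious events. Under 7.2.3 the duty to follow those ends at resolution or stabilisation, or at 30 days after the last dose, whichever comes first. That is about when the follow-up visit takes place, so little is lost. For SAEs the duty runs on, and the two sections part company.

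Long-term safety and tolerability is the primary objective, and deaths and SAE outcomes are what a reader of the report looks at first. The exposed interval runs from a subject's own follow-up visit to database lock. It is longest for subjects who stop early, because SAP 4.3 places the final analysis after the last subject's final follow-up visit.

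**Working it through.** The plan states no figure on this point, so there is none to reproduce. The check is to trace one event through the text.

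**Inputs**
- Onset before the follow-up visit, so the event is inside the window of Protocol 7.2.2 and on the eCRF AE page (Protocol 7.1.1).
- Unresolved at the follow-up visit, 30 (+7) days after the last dose (Protocol 3.1).
- Fatal afterwards, and reported to the Sponsor before database lock.

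**Trace**
1. Onset: the event enters the eCRF as an SAE, with a CTCAE grade below 5.
2. Follow-up visit: the outcome is set to ongoing, and 7.3 ends eCRF recording.
3. Death: the site, still following the event under 7.2.3, sends the information to the Sponsor under 7.4. Nothing tells anyone to change the eCRF, and 7.3 says not to.
4. Lock and analysis: SAP 5.3 takes the data as collected. SAP 4.3 wants all relevant study data integrated first, but does not say whether the Sponsor's SAE reports are included.

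**Effect on each planned output**

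| Output | If built from the closed eCRF record | If reconciled with the Sponsor's reports |
|---|---|---|
| SAE incidence (SAP 11.2.1) | subject counted once | subject counted once |
| SAE listing, outcome | ongoing | fatal |
| Severity summary (SAP 11.2) | pre-death grade | Grade 5 (Protocol 7.1.1) |
| Death listing (SAP 11.2) | no entry | one entry |

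For incidence, let x be the number of subjects with an SAE and N the number in the Safety Analysis Set. Both routes give x/N, so the difference is x/N − x/N = 0. The other three rows differ, each by one subject per such event.

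**What decides between the columns.** No sentence does. Three places point towards the eCRF: the recording stop in 7.3, the rule in SAP 5.3, and SAP 1, which lists the CRFs among the documents reviewed and mentions no safety database. Two leave the other route open: SAP 4.3, and Protocol 9.3, which has clinical data not on the eCRF captured and transferred to the Sponsor.

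**The case against.** The strongest reply is that the plan is silent here and does not exclude these data. SAP 4.3 does not limit the analysis database to eCRF data, and SAP 8.1.3 already merges bioanalytical laboratory results with database records. Protocol 9.3 provides for data held outside the eCRF, and a data-management plan that we cannot see may cover SAE reconciliation. This stands as far as it goes: the listings *can* be wrong, and it cannot be said that they *will* be. But permission is not a requirement, and 7.3 takes exactly these updates out of the ordinary route.

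A second reply is that a cutoff about 30 days after the last dose is legitimate. It is, for deciding which events are collected. The event traced here began before the cutoff; only its ending is lost, and 7.2.3 asks for that ending.

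A third is that follow-up may stop early, since 7.2.3 also lets it end on stabilisation or by agreement between investigator and Sponsor. In that case no later outcome may be known, and ongoing would be a fair entry. The point concerns only outcomes the Sponsor does hold before lock.

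Safety reporting itself is intact, because the Sponsor receives the information promptly. The weakness lies in the study outputs.

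**Conclusion.** The point holds for SAEs with onset inside the reporting window that are unresolved at the follow-up visit. For these, a fatal outcome known before lock can be shown as ongoing, at a pre-death grade, and be absent from the death listing. The size is one subject's outcome, severity grade and death entry per such event. This assumes that such an event occurs, that the Sponsor learns the outcome before lock, and that no unseen procedure already reconciles the two sources.

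A reader might infer more, and the documents do not support it:

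- *That an event rate is understated by one subject in nine (1/9 = 11.1%).* The SAE is already in the numerator, and SAP 11.2 plans deaths as a listing, not a rate.
- *That related SAEs starting after the study are wrongly left out.* Protocol 7.2.2 says of these: "If a subject experiences an SAE that is considered to be related to study treatment at any time after the study, it must be reported". The recipient is the Sponsor. They begin after the stated window, so their absence from study tables follows the cutoff. No sentence forbids showing them.
- *That a birth defect after a reported pregnancy would be a lost subject-level event.* The child is not in the Safety Analysis Set, and Protocol 7.2.5 gives pregnancies their own reporting route.
- *That years of SAE outcome data are bound to be lost.* That needs an early exit and an SAE still under follow-up for the rest of the study, which nothing in the documents makes likely.

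No dose, schedule or treatment rule is involved.

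**What to change.** In SAP 11.2 and 11.2.1, add that for every SAE ongoing at the follow-up visit, the outcome, severity grade and any death are reconciled with the Sponsor's SAE reports up to database lock. Carry the reconciled values into the SAE listing, the severity summary and the death listing, flagged as information received after follow-up. State the cutoff date used.

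The alternative is to amend Protocol 7.3 so that the SAE outcome field in the eCRF stays open until lock, which would also bring it into line with 7.2.3.

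Optionally, list related SAEs with onset after the follow-up visit separately, outside the treatment-emergent counts.

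The first route costs a few lines of SAP text and a small reconciliation task at lock, using reports the Sponsor already receives. The second needs a protocol amendment. Neither asks anything further of subjects.

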7.4.1 Investigator Reporting: Notifying the Sponsor

Any SAE, IAR or unanticipated problem posing risk of harm to subjects, must be reported to the Sponsor, or designee, within 24 hours of the event. To report such events, a SAE or IAR form must be completed by the Investigator and sent to the Sponsor within 24 hours. The Investigator will keep a copy of this SAE or IAR form on file at the study site. Report SAEs and IARs by phone, fax or email to:

For cases in North America	For cases in Europe
Phone: PPD	Fax: PPD
Fax: ^{PPD}	Email: PPD
Email: ^{PPD}	

The Investigator must promptly provide further information on the SAE, IAR, or the unanticipated problem. This should include a copy of the completed SAE or IAR form, and any other information that will assist the understanding of the event. Significant new information on ongoing SAEs or IARs must be reported to the Sponsor or designee immediately and no later than 24 hours of the Investigator's knowledge.

7.4.2 Investigator Reporting: Notifying the IRB/IEC

Unanticipated problems posing risks to subjects or others as noted above will be reported to the IRB/IEC per their institutional policy. Copies of each report and documentation of IRB/IEC notification and acknowledgement of receipt will be kept in the Investigator's study file.

7.4.3 Sponsor Reporting: Notifying Regulatory Authorities

The Sponsor is required to report certain study events in an expedited manner to the FDA, the European Medicines Agency, and to all country Regulatory Authorities where the study is being conducted. The following describes the safety reporting requirements by timeline for reporting and associated type of event:

Within 7 calendar days

Any study event that is:

associated with the use of the study drug, unexpected, fatal or life-threatening.

Within 15 calendar days

Any study event that is:

associated with the use of the study drug, unexpected, and serious, but not fatal or life-threatening.

7.4.4 Notifying Participating Investigators

It is the responsibility of the Sponsor or designee to immediately notify all participating Investigators of any suspected AE associated with the use of the drug that is both serious and unexpected, as well as any finding from tests in laboratory animals that suggest a significant risk for human subjects.

7.5 Medical Monitoring

It is the responsibility of the Investigator to oversee the safety of the study at his/her site. This safety monitoring will include careful assessment and appropriate reporting of AEs as noted above, as well as the construction and implementation of a site data and safety-monitoring plan (see Section 9). Medical monitoring will include a regular assessment of the number and type of SAEs.

7.5.1 Independent Safety Committee

Additional oversight of subject safety will be provided by an independent Safety Committee (SC) comprised of individuals with pertinent medical expertise who will serve in advisory capacity to the Sponsor to ensure that clinical trial participants are not exposed to unreasonable or unnecessary risks.

Collectively, the SC members will have methodological and clinical expertise relevant to the study design and population. SC membership will begin before the start of the clinical trial and is expected to last for its duration. Core members of the SC will not participate in the trial as Investigators or sub-investigators, as members of any team otherwise participating in the trial, or in any other capacity that may compromise their privileged activities on the SC. Neither members of the SC nor their immediate families will have a direct financial interest in the Sponsor or an interest that is dependent on the outcome of the trial. To be considered for SC membership, all candidates must disclose all actual or potential conflicts of interest, including any financial interests in, or research activity on a competing product. SC members will be compensated at an appropriate market rate for time spent reviewing, discussing, and attending the meetings. The Sponsor will also reimburse SC members for any out-of-pocket travel expenses required for attendance at the meetings. Aside from the above, SC members will receive no additional compensation for their membership on the committee.

The SC will perform periodic reviews of aggregate safety data from study LAL-CL04 on at least a biannual basis (i.e., every 6 months) from the date of enrollment of the first subject until completion of dosing for all subjects in the study. Ad-hoc reviews of safety data will also be performed by the SC on an as needed basis in the event of emerging safety signals of clinical concern in one or more subjects, including potential safety risks that meet the pre-defined stopping rules for study treatment (see Section 7.6). Following each periodic and ad-hoc review of safety data, the SC will indicate whether dosing of sebelipase alfa may continue (or be resumed) for all subjects or a subset of subjects in the study.

The composition and activities of the SC will be outlined in the SC Charter, which will be ratified during the initial meeting of the SC and prior to commencement of dosing in the extension study.

7.6 Dose Modification and Stopping Rules

The Sponsor or independent SC (see Section 7.5.1) may suspend dosing at any time for an individual subject, a cohort of subjects receiving a given dose, or all subjects enrolled in the study due to poor tolerance or potential safety risks.

Possible reasons for suspending dosing in an individual subject include SAE(s), Grade 3 (severe) or higher IAR(s). Specific dose modification and stopping rules for study LAL-CL04 are provided in Appendix E.

8 Statistical Plan

The Sponsor will be responsible for data collection and editing, reviewing and validating all the information in the eCRFs, statistical analysis, and generation of the clinical study report.

Prior to locking the database, all data editing will be complete and decisions regarding the evaluability of all subject data for inclusion in the statistical analysis will be made. The rationale for excluding any data from the statistical analyses will be prospectively defined, and classification of all or part of a subject's data as non-evaluable will be completed and documented before the entire database is locked.

A separate Statistical Analysis Plan (SAP) will be finalized prior to locking the database. The SAP will document any changes from the analyses as specified in the protocol and its amendments. The final clinical study report will document any changes from the SAP. The analysis will be performed using the SAS[®] statistical software system. If appropriate, other commercially available software may be utilized for graphical presentations.

8.1 General Considerations

All data collected in this study will be provided in subject data listings sorted by subject number. Data collected in this study will be reported using summary tables and graphs as appropriate to the data. Descriptive summary statistics (n, mean, median, standard deviation, minimum and maximum) will be calculated for the continuous variables and shift tables and/or frequencies and percentages will be produced for the categorical variables. As noted, 95% two-sided confidence interval (CI) will be calculated around the estimates based on the exact binomial distribution for categorical endpoints and the t-distribution for continuous endpoints. Effect of anti-drug antibodies will be examined for efficacy, safety, and PK endpoints. Numbers permitting, analyses may be conducted in other subgroups of interest.

Baseline will be defined as the last measurement prior to the first infusion of sebelipase alfa in study LAL-CL04. As appropriate, a CL01 Study Baseline defined as the last measurement prior to the first infusion in study LAL-CL01, may also be used for selected study endpoints. For endpoints that are computed as changes from baseline, a comparison between change from Baseline and change from the CL01 Study Baseline will be performed, as appropriate.

Unless otherwise noted, all tabulations will present data overall and by dose and dosing frequency (qw, qow) - i.e., dosing regimen.

8.2 Determination of Sample Size

Sample size is based on the estimated total enrollment in study LAL-CL01, and assumes that all subjects treated in that study will be eligible and willing to participate in this extension study.

8.3 Analysis Sets

Full Analysis Set (FAS): This analysis set consists of all subjects who received at least one complete infusion of IMP in the extension study, and have at least one post-treatment measurement in the extension study. This analysis set will be used for analysis of efficacy, pharmacodynamic, and patient health outcomes data.

Safety Analysis Set: This analysis set consists of all subjects who received any amount of IMP in the extension study, and will be used for all safety analyses.

Per-Protocol Analysis Set: This analysis set will consist of all subjects in the FAS who have no protocol violations that could potentially confound the interpretation of serum transaminase or lipid results. The list of subjects to be included in the per-protocol analysis set will be determined before database lock. If all patients in the FAS are also in the per-protocol analysis set, then separate analyses for the per-protocol analysis set will not be performed.

PK Analysis Set: This analysis set will include all available sebelipase alfa serum concentration data for subjects who receive at least one complete infusion of IMP in the extension study, and will be used for all PK analyses.

